3.9.2 Procedures for discontinuation of a patient from IP

A patient that decides to discontinue IP will always be asked about the reason(s) and the presence of any AEs. Diaries and all study drugs should be returned by the patient.

All patients who discontinue study drug will be asked to remain in the study for FU and complete all scheduled study visits through Week 27. At the time of discontinuation the Week 24 procedures will be performed. Patients will not receive double-blind study drug during this follow-up period (and use of SGLT2-inhibitors should be restricted), but will complete all scheduled study visits and procedures. Patients unable or unwilling to return for scheduled visits as part of follow-up will have the opportunity to receive follow-up via telephone calls placed by the site mainly to review safety and concomitant medications. The only exception to this procedure is when a patient withdraws consent for all study procedures or loses the ability to consent freely (i.e., is imprisoned or involuntarily incarcerated for the treatment of either a psychiatric or physical illness).

If a patient is withdrawn from study, see Section 3.10.

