7.7 Concomitant and other treatments

Changes in concomitant medication should be avoided during study participation, with the exception of situations defined in this protocol, but medication, which is considered necessary for the patient's safety and well-being, may be given at the discretion of the investigators, who must decide if the patient should remain in study or need to be dismissed from study due to patient's safety or interference with study objectives.

The administration of all medication must be recorded in the appropriate sections of the electronic CRF. The specific type of medication (trade or generic name), the indication for use, dosages, and the dates of usage should be reported.

After having completed or discontinued the study, patients will receive usual care and anti-diabetic agents according to the investigator's judgment and according to local medical practice.

Restricted Medication/Class of drug:	Usage:
Metformin	A metformin dose which is outside the specified dose range for moderate renal impairment (eGFR 30– 59 mL/minute/1.73m ² , MDRD formula) according to local guidelines or investigator's judgment, is not allowed.

Teriparatide, bisphosphonates and/or calcitonin	Treatment with teriparatide, bisphosphonates and/or calcitonin are allowed provided the dose has not changed within 30 days prior to enrolment.
---	---

Prohibited Medication/Class of drug:	Usage:
Antiviral drugs	Treatment for HIV and/or use of antiviral drugs (delavirdine, indinavir, nelfinavir, ritonavir, saquinavir) is not allowed
Glucocorticoids (long term treatment)	Long term treatment with glucocorticoids (equivalent to oral prednisolone ≥ 10 mg (betamethasone ≥ 1.2 mg, dexamethasone ≥ 1.5 mg, hydrocortisone ≥ 40 mg) is not allowed, (two temporary periods of no longer than 10 days each are allowed during the study); topical or inhaled corticosteroids are allowed.
Weight loss medication	Use of weight loss medication, including but not limited to sibutramine, phentermine, orlistat, rimonabant, benzphetamine, diethylpropion, methamphetamine, liraglutide indicated for anti-obesity treatment, and/or phendimetrazine, within 30 days of the enrolment visit, is not allowed.

Rescue/Supportive Medication/Class of drug:	Usage:
Open label rescue medication	See Section 4.3.3.1

Guidelines with regard to standard of care and other therapy

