### **2.1.5 Per Protocol (PP) Analysis Set**

The PP Analysis Set is a subset of the Full Analysis Set and will consist of patients who do not deviate from the terms specified in Appendix A (important protocol deviation), which may affect the study outcome significantly and interpretation of the study results. All decisions to exclude patients from the primary data set will be made prior to the unblinding of the study.

The PP Analysis set will only be applied if the PP Analysis set has a minimum of 10% fewer patients than the Full Analysis Set due to important protocol deviations. In that case, only the primary efficacy endpoint of change from baseline in HbA1c will be analyzed using the PP Analysis set. Demographics, and baseline diabetes characteristics will be summarized using the PP Analysis set if necessary.

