#### 4.1.3 Derivation of Efficacy Variable at Rescue/ Premature Discontinuation

In efficacy analyses, the glycemic parameters will only include measurements obtained prior to or on the date of rescue medication administration or discontinuation of double-blind medication (whichever is earlier). An exception would be in sensitivity analysis, where the analysis is performed on data regardless of rescue (see more details in Section 4.2.6.2).

For secondary efficacy variables of body weight (kg), seated SBP (mmHg) and remaining exploratory variables, measurements after rescue medication will not be excluded from the analyses.

Patients not completing the treatment period should have all Week 24 visit procedures done at the time of study discontinuation or rescue.

Patients who meet the pre-specified rescue criteria, at the specified visit described in Table 4, will be scheduled for a follow-up visit (within 3-5 days) to obtain a confirmatory central lab FPG value. If the confirmatory FPG value still meets the criteria, the patient will be rescued.

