**4.1.7.1 Multiple Imputation based on Retrieved Drop-outs (MI-RD)**

In MI-RD, all patients in the randomized set who have a baseline assessment (regardless of rescue or treatment discontinuation) will be included in the analysis. Based on status of whether the patients have early treatment discontinuation and whether the assessment is available at Week 24, the population will be categorized as 4 subpopulations described in [Table 6](#).

The main steps of the implementation of MI-RD are described below.

Step 1: Impute missing data for patients without HbA1c at Week 24 using a regression model imputation based on data from patients who discontinued treatment but had HbA1c assessment at Week 24 within that treatment group. The HbA1c baseline will be used as explanatory variable for imputation. If, for each (protocol-defined) visit where there is at least 1 patient with a last on-treatment assessment and is missing a Week 24 HbA1c value, there are (at that same visit) sufficient numbers of patients with a last on-treatment assessment that subsequently discontinued treatment but have a Week 24 HbA1c value, then the missing Week 24 HbA1c values will be imputed from the non-missing Week 24 HbA1c values by “last on-treatment visit” within each treatment group. Otherwise, if there are sufficient numbers of patients that discontinued treatment but have a Week 24 HbA1c value (regardless of last protocol-defined visit “on-treatment”) then missing Week 24 HbA1c values will be imputed from the patients that have discontinued treatment but have Week 24 HbA1c values within each treatment group. The imputation population and process are described in [Table 6](#). Imputation will be done within each treatment group.

Step 2: Analyze the multiple imputed HbA1c change from baseline at Week 24 using ANCOVA model. Combine estimates obtained from multiple imputed datasets based on Rubin’s combination rules ([Little R., Rubin D.B. 2002](#)).

The MI-RD approach requires a sufficient number of patients who discontinued treatment but had HbA1c assessment at Week 24 in each treatment. If there is not a sufficient number of patients to do the analysis, then this approach will not be implemented.

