**4.1.7.2    Washout Imputation**

In washout-imputation, all patients in the randomized set who have a baseline assessment (regardless of rescue or treatment discontinuation) will be included in the analysis. This imputation method will only impute the time point at Week 24 for the active treatment using multiple imputation regression with randomization strata and baseline HbA1c as the predictors. This approach ignores any post-baseline changes in the HbA1c values when predicting missing Week 24 values and will impute all patients similar to an average placebo patient. ANCOVA will be used as the analysis method.

The main steps of the implementation of the washout imputation are described below.

Step 1: Impute Week 24 missing data for patients in the active treatment using regression model multiple imputation based on data from the placebo arm. For patients in placebo arm missing data at any time point will be imputed assuming MAR mechanism. The variables used as explanatory variables for imputation include Randomization strata and HbA1c baseline.

Step 2: Analyze the multiple imputed data at Week 24 using ANCOVA model. Combine estimates obtained from multiple imputed datasets based on Rubin’s combination rules ([Little R., Rubin D.B. 2002](#)).

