#### 4.2.6 Efficacy Variables

##### 4.2.6.1 Primary Efficacy Variable

The primary objective of this study is to compare the mean change from baseline in HbA1c between dapagliflozin 10 mg and placebo, after 24 weeks of oral administration of double-blind treatment in patients with type 2 diabetes and CKD stage 3A. The primary estimand will be the treatment difference at Week 24 if all patients had remained in the trial and received treatment as planned without rescue medication. The analysis of the primary estimand will include all available data up to Week 24 or premature discontinuation of randomized treatment, whichever occurs first.

The null and alternative hypotheses of interest are:

$$H_0: \mu_s = \mu_p \text{ VS } H_a: \mu_s \neq \mu_p,$$

Where  $\mu_s$  and  $\mu_p$  are mean change from baseline to week 24 in HbA1c for study medication dapagliflozin and placebo groups respectively.

For rescued patients, measurements obtained after rescued medication or rescued insulin will be excluded. For patients discontinuing double-blind medication, measurements obtained after discontinuation will be excluded.

The primary analysis for the change in HbA1c from baseline at Week 24 will be based on longitudinal repeated measures analysis as described in Section 4.1.6.1. For all patients that are administered rescue therapy or discontinue treatment during the double-blind treatment period, only those measurements made on or prior to rescue or treatment discontinuation, (whichever occurs first) the will be included in analysis. For the primary efficacy analysis, the additional 3-way interaction term Baseline\*Week\*Treatment will be used as a model check to assess if there is statistically significant treatment effect across visits which differs in dependency on baseline values.

Point estimates and 95% confidence intervals for the mean change within each treatment group as well as for the differences in mean change between dapagliflozin 10 mg treatment group and the placebo treatment group will be calculated. P-value will be calculated to compare the treatment effect in the dapagliflozin 10 mg treatment group to that in the placebo treatment group.

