**Table 11 Summary of Analyses to Meet Secondary Efficacy Objectives**

Analysis type	LOCF or Observed values	Analysis set
Repeated measures mixed model of percent change from baseline to Week 24 in body weight (kg) (prior to treatment discontinuation)	Observed values	FAS
Repeated measures mixed model of change from baseline to Week 24 in FPG (mg/dL (prior to rescue and treatment discontinuation)	Observed values	FAS
Repeated measures mixed model of change from baseline to Week 24 in seated SBP (mmHg) (prior to treatment discontinuation)	Observed values	FAS

LOCF = Last Observation carried Forward; FAS = Full analysis set

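### Protocol 7.7 lets an investigator dismiss a randomised patient from the study over a needed medicine, against the retention rule in 3.9.2; make it a stop-drug decision and keep the visits

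*Protocol*

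**What the plan says.** Protocol 7.7 allows medicines needed for a patient's safety or well-being at the discretion of the investigators, "who must decide if the patient should remain in study or need to be dismissed from study due to" one of two reasons: the patient's safety, or interference with what the study sets out to measure. The exit described is from the study, not from study drug.

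Protocol 3.9.2 asks every patient who stops study drug to stay and complete visits through Week 27. It then says: "The only exception to this procedure is when a patient withdraws consent for all study procedures", or loses the ability to consent freely. Table 1 footnote e and section 4.3.5 also keep such patients on the ordinary visit schedule unless they withdraw consent entirely. Section 3.10 lists screen failure (non-randomised patients only), withdrawal of consent and loss to follow-up.

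On analysis, SAP 4.2.6.1 uses "only those measurements made on or prior to rescue or treatment discontinuation" for HbA1c. SAP Table 11 cuts weight and blood pressure only at treatment discontinuation, for example "Repeated measures mixed model of change from baseline to Week 24 in seated SBP (mmHg) (prior to treatment discontinuation". Two sensitivity analyses, retrieved-dropout imputation (MI-RD) and washout imputation, use HbA1c regardless of rescue or discontinuation.

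**The concern.** Safety can justify stopping a drug. Interference with the study's aims is a different kind of reason: it ends observation of a randomised patient because of something that happened after randomisation. Elsewhere the protocol declines to do this. Rescued patients and those with insulin up-titration stay on schedule (4.3.3.1), and patients whose oral agents or insulin are reduced stay in the study on blinded treatment (7.7).

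If a site follows 7.7 literally, later visits are not collected and cannot be recovered. At stake are Week 24 HbA1c for the analyses that use values after discontinuation, and scheduled safety follow-up. Retained values can always be set aside in an analysis; uncollected ones cannot be added.

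**Working it through.** **1. The texts side by side (randomised patients).**

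- 7.7: the investigator may end study participation for safety or for interference with objectives.
- 3.9.2, Table 1 footnote e, 4.3.5: stopping drug does not end participation; 3.9.2 names withdrawn or lost consent as its only exception. This is an explicit conflict.
- 3.10: no matching exit route, but the list is not said to be exhaustive. This is a conflict by omission only.
- During the placebo lead-in, dismissal can be compatible with screen failure under 3.10.1, so the conflict concerns randomised patients.

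**2. What dismissal loses.** SAP 4.1.3 says: "Patients not completing the treatment period should have all Week 24 visit procedures done at the time of study discontinuation or rescue". An exit value therefore exists. Under SAP Table 17 it counts as Week 24 only from Day 128. Earlier exits leave the Week 24 window empty.

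- MI-RD: "The MI-RD approach requires a sufficient number of patients who discontinued treatment but had HbA1c assessment at Week 24 in each treatment" group, and it is not run if there are too few.
- Washout imputation still runs, but a dismissed dapagliflozin patient's missing value is then filled by a model that "will impute all patients similar to an average placebo patient".
- Primary repeated-measures model: unchanged for a patient taken off drug, because later values are excluded anyway.

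**3. The plan's own sample size.** Inputs from Protocol 8.2: difference 0.3, SD 0.9, two-sided alpha 0.05, two-sample t-test, 80% power, 5% not evaluable.

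- Required n per group: 142.25, rounded up to 143; power at 143 is 80.2%.
- 143 / 0.95 = 150.5, so 151 per group and 302 in total.

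The stated figures reproduce.

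**4. Size of the loss.** No dismissal rate is given. Assume 1 to 5% of 302 (3 to 15 patients), with exits spread evenly over Days 2 to 169.

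- Share of exits on Days 2 to 127: 126 / 168 = 0.75.
- Week 24 values lost: 302 × 0.01 × 0.75 = 2.3, to 302 × 0.05 × 0.75 = 11.3.

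**5. Power if those values are simply lost** (a worst case: every such patient would otherwise have stayed on drug, and the repeated-measures model is given no credit for earlier values).

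- 1%: n = 143 × (1 − 0.0075) = 141.9 per group, power 79.9%.
- 5%: n = 143 × (1 − 0.0375) = 137.6 per group, power 78.7%.

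**6. Power if the patients are kept on drug.** Assume the added medicine shifts HbA1c by 1.0 point in a fraction p of both arms. SD = √(0.81 + p(1 − p) × 1.0²).

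- p = 0.01: SD = √0.8199 = 0.905, power 79.7%.
- p = 0.05: SD = √0.8575 = 0.926, power 77.9%.

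On these assumptions retention does no better for power than dismissal. The case for it rests on completeness.

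**7. Existing handling of interfering medicines.** Protocol 8.3.4 provides complete or partial exclusion from the per-protocol set for medicines prohibited in 7.7. SAP 2.1.5 says that set "will only be applied if the PP Analysis set has a minimum of 10% fewer patients" than the Full Analysis Set, and then only for HbA1c. The shortfall is 29 of 286 patients (10% is 28.6), or 15 of 143 in one arm under SAP 4.2.6.2 (10% is 14.3). It counts all important deviations.

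**The case against.** The strongest reply is that retention is already specified. A dismissed patient also stops drug, so 3.9.2, Table 1 footnote e and 4.3.5 apply, and Protocol 1.4 sends patients who discontinue treatment into the safety follow-up. Three specific procedures should outweigh one general clause, and 7.7.1 lets other necessary medicines be given and simply recorded. On this view the defect is editorial. That is a fair reading of intent. It does not remove the instruction in 7.7, which tells the investigator to decide about the study itself and offers a non-safety reason for ending it.

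It also stands that few patients are affected, that power does not favour the change, and that keeping patients on drug lets the effect of, say, a long-term steroid into a primary analysis whose estimand assumes treatment as planned.

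A reader might infer more than the documents support:

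- **Biased exit.** Investigators see on-treatment FPG, so exit might seem to depend on outcome. But they are blinded to allocation and HbA1c, high FPG leads to rescue with retention, and nothing links FPG to decisions about other medicines. Any bias is of unknown size and direction.
- **No per-protocol protection at all.** Three to 15 patients alone would rarely reach the 10% threshold, but all important deviations count towards it, so whether it is met is unknown. Appendix A is redacted, so the classing of each medicine cannot be checked.
- **Loss of the post-treatment eGFR outcome.** For someone who stopped drug on Day 60, the Week 27 visit (Day 190) is 190 − 60 = 130 days later. That is useful safety follow-up, but not the 3-week post-treatment measure in Protocol 2.3.

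**Conclusion.** The point holds as an inconsistency worth correcting at low cost. For randomised patients, 7.7 conflicts explicitly with 3.9.2, Table 1 footnote e and 4.3.5; 3.10 is merely silent. The benefit of correcting it is more complete Week 24 HbA1c for MI-RD and washout imputation (about 2 to 11 values, on an assumed 1 to 5% dismissal rate with even timing) and more complete safety follow-up. The text does not support a claim that the primary result is at risk: the primary model is unchanged for patients taken off drug, and the power differences are small and do not favour retention. The missing sensitivity analysis for interfering medicines is secondary. For HbA1c the conditional per-protocol analysis partly covers it; for weight and blood pressure no listed analysis does.

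**What to change.** In Protocol 7.7, for randomised patients:

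- Replace the dismissal clause with a decision on whether to stop study drug for safety under 3.9.
- Delete interference with objectives as a ground for leaving the study.
- State that scheduled visits and efficacy and safety collection continue through Week 27 under 3.9.2 unless consent is withdrawn or lost.

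Align two other sentences: 1.2 describes the rescue criteria as leading to withdrawal from the study, although rescued patients continue under 4.3.3.1; and 3.9.1 speaks of leaving the study for severe hypoglycaemia where stopping study drug is meant.

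Optional SAP supplement: a sensitivity analysis of HbA1c, weight and seated systolic pressure that excludes values after the start of an interfering medicine, with the list fixed before unblinding. It answers the main drawback of retention, that on-drug values may carry the added medicine's effect.

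Cost: one clause, two sentences and, if wanted, one analysis using medication dates that 7.7 already requires. A few patients attend visits already on the schedule. The planned 302 is unchanged.

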7.7.1 Other concomitant treatment

Other medication other than that described above, which is considered necessary for the patient's safety and well being, may be given at the discretion of the Investigator and recorded in the appropriate sections of the CRF.

7.8 Post Study Access to Study Treatment – Not Applicable

8. STATISTICAL ANALYSES BY ASTRAZENECA

8.1 Statistical considerations

- All personnel involved with the analysis of the study will remain blinded until database lock and protocol violators identified.
- Analyses will be performed by AstraZeneca or its representatives.
- Refer to SAP for details.
- All personnel involved with the analysis of the study will remain blinded until database lock and protocol violators are identified. Analyses will be performed by AstraZeneca or its representatives.

A comprehensive Statistical Analysis Plan (SAP) will be prepared prior to first patient randomized and any subsequent amendments will be documented, with final amendments completed prior to unblinding of the data (this is the expectation for the pivotal studies).

8.2 Sample size estimate

The primary endpoint is the change from baseline in HbA1c at Week 24. From post-hoc results of similar clinical studies (Study MB102029, Study D1690C00018, and Study D1690C00019) when patients meeting eGFR entry criteria like those in this current study were selected, the mean placebo-corrected change from baseline in HbA1c after 24 weeks of treatment for the current study is estimated to be -0.3% for dapagliflozin 10 mg.

Assuming a common standard deviation (SD) of 0.9% in the primary endpoint, 143 patients per treatment group with both baseline and at least one post-baseline HbA1c measurement will provide 80% power to detect a treatment difference of 0.3% in the primary endpoint at a two-sided significance level =0.05, using a two-sample t-test. Assuming that 5% of randomized patients fail to qualify for inclusion in the full analysis set due to missing baseline and/or all post-randomization values for this primary endpoint, a total of 302 randomized patients (151 per treatment group) are needed for the study.

8.3 Definitions of analysis sets

8.3.1 Enrolled Patients Data Set

The Enrolled Patients Data Set includes data collected from all patients who signed informed consent.

8.3.2 Lead-in Patients Data Set

The Lead-in Patients Data Set includes data collected from all patients who took at least one dose of lead-in medication.

8.3.3 Full Analysis set

The primary efficacy analysis will be performed on the Full Analysis Set, which will consist of all randomized patients who took at least one dose of double-blind study drug during the short term double-blind period and have a non-missing baseline value and at least one post-baseline efficacy value (HbA1c, total body weight, FPG, and SBP).

When the Full Analysis Set is used, patients will be presented in the treatment group to which they were randomized at the start of the short term double-blind treatment period (even if the treatment they received was different).

